3.17. Main independent measures will be intervention condition: CTC or equal attention control group for Aims 1 & 2. For Aim 3, we will also evaluate three injection initiation social learning risks as mediating variables. These items are intended to capture social learning constructs (i.e., observation of behavior, supportive interactions, and reinforcement) within the social processes of injection initiation. To capture observing, we will ask current PWID the following item: "In the past 6 months, have you injected drugs in front of someone who has never injected an illicit drug?" To capture interaction, we will ask "In the past 6 months have you explained or described how to inject to someone who has never injected an illicit drug (i.e., a noninjector)?" To measure reinforcement we will ask, "In the past 6 months, have you spoken positively about injecting with someone who has never injected an illicit drug?" Each item is a binary variable (Yes/No) where Yes denotes endorsing the injection initiation social learning risk assessed.

We will also collect IMB constructs related to injection initiation and sex risk. For the information construct, we will collect true or false knowledge items on sex-related HIV prevention provided by Kalichman, Simbayi and others^{5,6} and develop similar items for injection initiation risks. To develop injection initiation risk motivation and behavioral skill items we will follow procedures outlined by Kalichman, Simbayi and others.^{5,6} For sex-risk related motivation and behavioral skill items we will draw from existing studies.^{5,6} All injection initiation risk and sex-related IMB skill items will all be pilot tested. Psychometric properties of existing measures are known and acceptable, however, we will test both existing and new measures for their applicability to this study population. Drafts of all items are provided in the baseline survey (**Appendix H**).

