3.18. Potential confounding variables or covariates will be selected from the following domains: sociodemographics/economics, current drug use patterns, blood borne infectious disease risks, experimental condition contamination, and social desirable responding. Socio-demographic and socioeconomic characteristics will be collected from each participant, including race/ethnicity (with options for multiple racial/ethnic identification), age, education, income/income sources, living arrangements (including homelessness), and relationship status. Drug use history and current use patterns have previously been shown to be associated with initiation of injection-naive people.⁵⁹ In the proposed study, we will assess frequency of injection and non-injection in the past 30 days for the following drugs: crack cocaine, cocaine, heroin, methamphetamines, speedball (admixture of heroin/cocaine), goofball (admixture of heroin/methamphetamines), prescription drug misuse (e.g., opiates, tranquilizers, stimulants, sedatives, methadone, and buprenorphine), and marijuana. The drug use items have been found to be valid and reliable.^{16,17} *Injection-related HIV and HBV/HCV risk* will be captured using modified items from NIDA's cooperative agreement study of the 1990s (the "RBA").⁹⁶ These items have been found to be valid and reliable.^{15,17} *Socially desirable response set measure* (SDRS-5) contains five items adapted from the Marlowe-Crowne Form A measure of social desirability. Respondents rank each item on a 4-point scale ranging from 1 (strongly disagree) to 4 (strongly agree).⁹⁷

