3.19. Six-month and 12-month follow-up measures will include all main outcome (**Section 3.16**.) and independent variables (**Section 3.17**) as well as socio-demographic and economic variables that could change during the 6-month follow-up periods (e.g., relationship status, homelessness, income). We will also assess contamination at 6-month follow-up interview. It is possible that skills learned by the CTC participants may be shared with participants in the equal attention control group. This type of contamination cannot be prevented, but it can be measured. At 6-month interview, participants in both conditions will be asked if they have had conversations with other PWID on a variety of health issues, including injection initiation, initiation injection social learning risk, sex risk, and other items to mask the intent of the question. We will also ask them about intervention phrases such as "Change the Cycle" to assess whether control group participants are familiar with them. A similar approach has been used in other intervention studies among PWID to identify exposure to an intervention.⁹⁸ We will ask questions about satisfaction with and usefulness of the CTC intervention or the equal attention control 12 month survey. The domain lists for items to be included in the 6 and 12 month survey are provided in **Appendix I**.

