5.0 SELECTION AND WITHDRAWAL OF SUBJECTS

- 5.1 Inclusion Criteria: Inclusion criteria for the baseline/screening interview are (1) recent injection of illicit drugs (past 30 days), as verified by checking for venipuncture marks,⁸⁴ (2) age 18 years or older, and (3) ability to provide informed consent.
- 5.2 Exclusion Criteria: Less than 18 years of age, no evidence of recent drug injection, inability to provide informed consent, and non-English speaking.
- 5.3 Withdrawal Criteria: Participants who unable to complete either the experimental or control condition intervention may be asked to withdraw from the study. Each participant will be given at least 2 opportunities to complete the one-hour educational session to which they were assigned.

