Aim 3: To test whether injection initiation social learning risks (injecting in front of, describing injection to, and speaking positively about injection to non-injectors) act as mediational mechanisms for the efficacy of the CTC intervention on initiation and request-to-initiate outcomes. H3: Social learning variables will significantly mediate the association between the CTC intervention and episodes of initiating and being requested to initiate someone into drug injection at 6 and 12 months. The outcome variable will remain counts of the number of episodes initiating someone into drug injection (Aim 1) and the counts of request to initiate another person (Aim 2). The mediational models will be specified following the work of Baron and Kenny and newer generalizations.¹⁰⁶⁻¹⁰⁸ With only three time points, we can examine the effect of baseline randomization to treatment status on 12-month counts of injection initiation as the outcome and 6-month injection-risk behavior variables as the mediators. The lagged approach can be used as static measures at 6 months and 12 months, or changes in injection initiation social learning risks and IMB skills constructs that precede changes in the number of counts of initiation as outcome. This latter approach is strong in that the change in a variable, created by difference scores, is isolated so that it precedes the subsequent outcome.

There are also techniques for estimating mediational models with only 2 time-points;¹⁰⁹ consequently, we will examine mediation from randomization to 6-month follow-up with the mediator and outcome measured concurrently. We can estimate separate mediational models for each injection initiation social learning risk and IMB skills construct, or enter the mediation mechanisms together into a single model, while examining overfit due to multiple mediational paths.¹¹⁰ Omnibus measures of model fit (chi-square, root mean square error of approximation, Tucker Lewis Index [TLI]), and specific path coefficients will be used to assess the treatment effect and test for the mediational pathways. The null hypothesis will be rejected if the p value for the variable that denotes treatment condition is below 0.05. Proposed Co-I [name] has extensive experience with these techniques as part of longitudinal community-based interventions.^{105,111,112}

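### H3 names no adjustment for the participant's own injecting after baseline, and section 3.19 does not name it as a follow-up measure, so mediation could appear where none exists

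*Combined protocol and SAP*

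**What the plan says.** Section 3.19 says the 6- and 12-month interviews will include the section 3.16 outcomes and the section 3.17 independent variables, "as well as socio-demographic and economic variables that could change during the 6-month follow-up periods (e.g., relationship status, homelessness, income"). It adds contamination items at 6 months and satisfaction items at 12 months. It does not cite section 3.18, where own drug use sits. For the full content it refers elsewhere: "The domain lists for items to be included in the 6 and 12 month survey are provided in" Appendix I, of which only the title was available.

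Section 3.18 plans to measure own drug use: "we will assess frequency of injection and non-injection in the past 30 days for the following drugs". It gives no time point. Among the covariate domains it lists "current drug use patterns, blood borne infectious disease risks, experimental condition contamination, and social desirable responding".

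Injecting is required only at entry. Section 5.1 asks for "recent injection of illicit drugs (past 30 days), as verified by checking for venipuncture marks". No section says how a participant who later stops injecting is to be handled. Section 3.16 recodes No and not-applicable answers on the initiation item to zero.

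For Aim 3, section 13.1 plans a lagged model with "12-month counts of injection initiation as the outcome and 6-month injection-risk behavior variables as the mediators", and a second model with mediator and outcome both measured at 6 months. The covariates named in section 13.1 are tied to baseline imbalance, loss to follow-up, fidelity and possibly site. None is named for the mediator-to-outcome path.

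**The concern.** Randomisation protects the path from arm to mediator. It does not protect the path from mediator to outcome, and a participant's own injecting after enrolment is a plausible common cause of both ends of that path. A person who did not inject in the window cannot truthfully say Yes to "In the past 6 months, have you injected drugs in front of someone who has never injected an illicit drug". That person also has less occasion to describe injecting, to speak well of it, to be asked for help, or to give someone a first injection.

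Baseline adjustment cannot remove this. Everyone was injecting at entry, so later inactivity does not vary at baseline.

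If CTC lowers the mediator and the mediator is associated with the outcome only through inactivity, H3 would report social learning risk as the mechanism when it is not. If CTC itself reduces own injecting, that is a rival pathway that the H3 model would partly credit to social learning. At stake is the explanation of how CTC works, not whether it works.

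**Working it through.** **Inputs from section 13.2**
- Retained sample: 1,076 x 0.75 = 807, against the stated figure of approximately 800. I use 400 per arm.
- Initiation rate: 431/809 = 0.533 per person per year. As a check, 1,076 x 431/809 = 573, as stated. Per 6 months the rate is 0.533/2 = 0.266.
- Expected effect on a mediator: a 38% reduction in injecting in front of injection-naive people.
- Two-sided alpha of 0.05.

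**Assumptions, because the documents give no figure**
- Share i not injecting in the window: 10% and 20%, with 0-30% as the wider range.
- Mediator prevalence p among injecting controls: 50%, varied from 30% to 70%.
- Inactive participants initiate nobody, and inactivity does not depend on arm.
- The mediator has no effect on the outcome.

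**Step 1. Spurious ratio by hand, mediator and outcome in the same window.** If inactive people always score No on the mediator and zero on the outcome, the ratio of mean counts (mediator Yes to mediator No) within an arm is

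ratio = [(1-i)(1-p) + i] / [(1-i)(1-p)].

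- Control arm, p = 0.50: i = 0.10 gives (0.45 + 0.10)/0.45 = 1.22; i = 0.20 gives (0.40 + 0.20)/0.40 = 1.50.
- CTC arm, p = 0.50 x 0.62 = 0.31: i = 0.10 gives (0.621 + 0.10)/0.621 = 1.16; i = 0.20 gives (0.552 + 0.20)/0.552 = 1.36.

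The true ratio is 1. H3 pools the arms, so the expected value lies between the two. Simulation gave medians of 1.19 and 1.44.

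**Step 2. False mediation, concurrent case.** Simulated trials with 400 per arm used Poisson regression of the count on arm and mediator with robust standard errors. Mediation was declared when the arm-to-mediator and mediator-to-outcome paths both had p < 0.05. Section 13.1 states its rejection rule for the treatment variable only, so this joint rule is an assumption. Inactivity covered both the mediator and the outcome. There were 2,000 trials per setting, with gamma dispersion 1 unless stated.

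| Not injecting | False mediation |
|---|---|
| 0% | 5.2% |
| 5% | 9.5% |
| 10% | 19% |
| 20% | 52% |
| 30% | 81% |

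Sensitivity of these results:
- Mediator prevalence 30%: 11% at 10% inactive and 28% at 20%. Prevalence 70%: 31% and 78%.
- At 20% inactive, dispersion 0 gives 60% and dispersion 3 gives 37%. A Sobel test gives 42%.
- Inactive people endorse the mediator half as often: 17% at 20% inactive. Equally often: 4.9%.
- CTC does not change the mediator: 3.2% at 20% inactive and 3.8% at 30%, so no inflation.

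**Step 3. Lagged model (6-month mediator, 12-month outcome).** Inactivity must now persist from the first window to the second. The ranges reflect how far it does; weaker persistence gives the lower end.

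| | 10% inactive | 20% inactive |
|---|---|---|
| Inactive people never endorse the mediator | about 12-21% | about 28-57% |
| They endorse it half as often | about 7-12% | about 12-15% |

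**Step 4. With own injecting measured.** Adding months 0-6 injecting to the H3 outcome model brings lagged false mediation back to about 3-7%.

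**The case against.** The strongest objection is that an omission has not been shown. Section 3.19 says what follow-up will include and leaves the full list to Appendix I. Section 3.18 gives no time point, and it is not a baseline-only list, because it includes contamination, which section 3.19 places at 6 months. A reader might infer that own injecting is collected once and then dropped. The documents do not support that. They show only that section 3.19 does not name it. What stands is that a past-30-day item, even if repeated, does not span a 6-month recall, and that Aim 3 names no use of it.

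A reader might also infer that people who stop injecting score No on every mediator and zero on the outcome. Only injecting in front of others is forced to No. Describing injection, speaking positively about it and helping with a first injection all remain possible. This matters for size, as the half-as-often figures show.

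Entry requires "recent injection of illicit drugs (past 30 days") and the items look back 6 months, so a person must go essentially the whole first window without injecting for the first mediator to be forced to No. Someone who stops in month 2 can still answer Yes. Shares of 20% or more may therefore be high. Some people in custody or residential care would be lost to follow-up rather than scored zero, and homelessness, which is measured, captures part of being out of the community. These points limit the magnitude but do not remove the mechanism.

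Finally, unmeasured mediator-outcome confounding is a general limit of mediation analysis, and section 7.1 describes Aim 3 as exploring mechanisms. That is fair, but this confounder is foreseeable and cheap to measure.

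**Conclusion.** The concern holds in a limited form. Own injecting after baseline is not specified in section 3.19, the section 3.18 item does not match the 6-month window, and the H3 models as written leave the mediator-to-outcome path open to confounding by stopping injecting.

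Under the stated assumptions, a nominal 5% error rate for lagged mediation becomes about 12-21% at 10% inactive and 28-57% at 20% if inactive people never endorse the mediator. It becomes about 7-12% and 12-15% if they do so half as often. The forced-No case applies directly only to injecting in front of others. The rate stays near 5% if nobody is inactive, and there is no inflation if CTC leaves the mediator unchanged. The inactive share, its persistence and the mediator prevalence are all assumed, so these are ranges and not predictions.

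A reader might extend this to the efficacy results. The documents do not support that: H1 and H2 compare randomised arms and do not depend on the mediator-to-outcome path.

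**What to change.** 1. State in section 3.19, and align Appendix I, that both follow-up interviews ask about own injecting, and about time in custody or residential treatment, over the same 6-month window as the outcomes.
2. In H3 only, include own injecting in months 0-6 in the mediator-outcome model, as a confounder or, since CTC may affect it, as a parallel mediator. Report H3 with and without it.
3. Treat any analysis restricted to people still injecting as a labelled sensitivity analysis. For the lagged model, define it on months 0-6 only, because injecting in months 6-12 follows the mediator. State that it selects on a post-randomisation variable.
4. Do not add the term to the H1 or H2 models.

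The cost is a slightly longer interview and one more term in the H3 models. The information would be hard to recover reliably once follow-up closes.

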CTC uses the Information-Motivation-Behavioral skills (IMB) model^{3,4} to achieve changes among active PWID through seven short modules. Information and motivational domains are addressed in guided conversations about (1) their own first injection episode and consequences, (2) past experiences initiating injection-naive people and consequences, (3) health, legal, and social risks related to injection drugs, (4) health, legal, social risks of initiating people, and (5) identifying their own behaviors that might promote injection among others. The behavioral skills domain is addressed through a (6) skill-building discussion and rehearsal of responses to possible initiation scenarios, and (7) safer injection education. CTC pilot study results found significant reductions in injection initiation episodes; however, the study did not have a control group.⁷ Our specific aims are:

Aim 1: To test the efficacy of CTC on reducing the number of non-injectors initiated into injection (counts) by PWID. *Hypothesis 1*: PWID who receive CTC will report initiating fewer non-injectors into drug injection at 6 and 12 months as compared with PWID in the equal attention control condition.

Aim 2: To test the efficacy of CTC on reducing the number of times PWID are asked to initiate (counts) someone into injection. Hypothesis 2: PWID who receive CTC will report having been asked fewer times to initiate someone into drug injection at 6 and 12 months as compared with PWID in the equal attention control condition.

Aim 3: To test whether injection initiation social learning risks (injecting in front of, describing injection to, and speaking positively about injection to non-injectors) act as mediational mechanisms for the efficacy of the CTC intervention on initiation and request-to-initiate outcomes. Hypothesis 3: Social learning variables will significantly mediate the association between the CTC intervention and episodes of initiating and being requested to initiate someone into drug injection at 6 and 12 months.

Following completion of 12-month follow-up interviews, we will collect elucidation interviews with up to 100 PWID for purposes of providing preliminary data on key issues related to 1) Hepatitis A and C risk, needs, and services collected through a quantitative survey, and 2) experiences with drug effects and withdrawal and symptoms management in a qualitative audio-recorded interview.

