3.15. Data collection measures. Data collection measures were selected based on their relevance to evaluating CTC, applicability to social learning theory and IMB model, and potential as confounders. Items from each area are described below and a draft of the baseline questionnaire is included in **Appendix H**.

3.16. Main outcome measures for **Aims 1 & 3** will be the number of people initiated in the past 6 months. This item will be assessed by asking the following questions: "In the past 6 months, have you helped someone get their first hit (the first time they ever injected)?" If participants respond Yes, they will be asked the following question: "How many people (total) have you helped get their first hit (inject for the first time) in the past 6 months?" Not applicable responses (or No on the first item) will be recoded as zeros for data analysis purposes. For **Aims 2 & 3** we will ask the following items: "In the past 6 months, have you been asked to help someone inject an illicit drug for the first time?" Participants responding 'yes', were then asked how many people had asked them to provide their first injection. The time frame of 6 months allows us to assess changes in the outcome at 6 months (as was done in the pilot) and 12 months. The use of a count approach for outcome variables enables us to account for changes even if they only occur among high volume initiators and those with multiple injection initiation social learning risk. We will also collect data on sex risk, specifically, unprotected sex, multiple sex partners, and sex risk by partner type^{91,92} for purposes of determining the efficacy of the attention control condition although this is not an aim of the proposed study.

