T1). There will be little need for additional covariates to control for potential inflation of the correlations due to recruitment sites, as the targeted sampling will ensure full coverage across the locations where PWID congregate in LA and SF. We will, however, explore differences between the two sites, and may introduce a control variable to account for large-scale environmental differences between the two sites. To avoid any analytic decisions being driven by a desire for a certain result, the statistician and data analysis team will be blinded as to whether 0 or 1 denotes the treatment or control condition until the analyses are completed. There is also potential for contamination, which we will assess by asking the respondents in the control condition their level of exposure to intervention components, as described in Section 3.5.17.3. We will follow procedures outlined by Keogh-Brown et al. (2007) using complier average causal models (CACE),¹⁰⁴ in which the bias associated with contamination is significantly reduced by averaging the estimated causal effect over classes of participants that differ in the level of exposure to contamination. Each person in the control group will be assigned to a class, depending on their level of exposure and type of exposure, using latent classification techniques utilized by [name] in previous publications.¹⁰⁵ Lastly, we will compare differences in examining the rate of change versus the standardized difference at each follow-up point (e.g., compare counts of injection initiation at 6m and 12m) and test for differences by condition. The latent change model has more power than the raw difference approach, and we will present differences in our published work if the outcome is sensitive to model estimation.

Aim 2: To test the efficacy of CTC on reducing the number of times PWID are asked to initiate (counts) someone into injection. H2: PWID who receive CTC will report having been asked fewer times to initiate someone into drug injection at 6 and 12 months as compared with PWID in the equal attention control condition. This model will be estimated in the same manner as the model for the outcome of the actual number of reported counts, save that this one will estimated using the self-reported counts by the respondent regarding being asked to initiate another person.

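### Contamination is asked about only at 6 months, so the contamination-adjusted (CACE) analysis of the 12-month counts would class controls first exposed in months 6 to 12 as unexposed

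*Combined protocol and SAP*

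**What the plan says.** Section 3.19 covers both follow-up visits but ties contamination to the first: "At 6-month interview, participants in both conditions will be asked if they have had conversations with other PWID". The questions cover several health topics, so that their purpose is masked, and also test familiarity with intervention phrases such as Change the Cycle. The one item the section adds specifically for the later visit is participant opinion: "We will ask questions about satisfaction with and usefulness of the CTC intervention or the equal attention control 12 month survey". For both visits it carries forward the outcomes (3.16), the independent variables (3.17) and those socio-demographics that can change. Contamination is listed among the covariate domains of 3.18 ("experimental condition contamination, and social desirable responding"), which 3.19 does not carry forward.

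Section 13.1, Aim 1, puts the answers to use. Each control is placed in a class by level and type of exposure, and the CACE model works by "averaging the estimated causal effect over classes of participants that differ in the level of exposure to contamination". Aim 2 is to be modelled in the same way. For the exposure questions, 13.1 points to Section 3.5.17.3. This document has no such section, so 3.19 is the only description available.

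Hypothesis 1 states that "PWID who receive CTC will report initiating fewer non-injectors into drug injection at 6 and 12 months", and Hypothesis 2 that "PWID who receive CTC will report having been asked fewer times to initiate someone into drug injection at 6 and 12 months". The outcome question has a six-month recall: "How many people (total) have you helped get their first hit (inject for the first time) in the past 6 months".

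**The concern.** The 12-month count covers roughly months 6 to 12, and no exposure question covers that window. A control who first hears CTC content in month 8 can be classed only from the month-6 answers, which truthfully say unexposed. Latent classification can sort recorded answers but cannot recover exposure that nobody asked about.

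Section 3.19 itself says that contamination cannot be prevented but can be measured, and Section 13.1 relies on CACE to reduce the bias. At 12 months that correction would be incomplete, and the data would not show by how much.

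**Working it through.** **Is late exposure plausible?** Section 3.9 gives about 48 baseline interviews a month. Assume that all are randomised, half to each arm.
- Accrual: 1,076 / 48 = 22.4 months, at 24 CTC participants a month.
- When the first controls reach month 6: 24 × 6 = 144 CTC participants, or 144 / 538 = 27%.
- When they reach month 12: 24 × 12 = 288, or 288 / 538 = 54%.
- Averaged numerically over all control enrolment dates, the CTC pool is about 335 in a control's months 0 to 6 and 440 in months 6 to 12. If contact is proportional to pool size, 440 / (335 + 440) = 57% of it falls in the window without a question.

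The growth varies by enrolment date. For controls enrolled last, the pool is already at or near 538 throughout.

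**Sample at 12 months.** Section 13.2 plans 25% attrition: 1,076 × 0.75 = 807, which agrees with the stated 800 or so, or about 400 controls.

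**Size of the under-correction.** The documents give no contamination rate, so there is no planned figure to reproduce. Let c be the share of controls exposed by month 6, and assume the same rate among those still unexposed in months 6 to 12.
- Newly exposed after month 6, as a share of all controls: c(1 − c).
- Share of the coded-unexposed class that is in fact exposed: c(1 − c) / (1 − c) = c.
- Suppose an exposed control gets the full CTC effect and exposure is unrelated to baseline risk. The CACE contrast at 12 months then recovers 1 − c of the true difference, and the unadjusted comparison by arm recovers (1 − c)².

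| c by month 6 | Newly exposed later | Of 400 controls | Unadjusted comparison recovers | CACE with month-6 classes recovers |
|---|---|---|---|---|
| 5% | 4.75% | 19 | 90% | 95% |
| 10% | 9% | 36 | 81% | 90% |
| 20% | 16% | 64 | 64% | 80% |

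Exposure recorded at both visits would recover 100% under the same assumptions.

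**On the plan's own scale.** Section 13.2 cites 431 initiations by 809 people in a year: 431 / 809 / 2 = 0.266 per person per six months, if spread evenly. Halving it gives a true difference of 0.133. The CACE contrast would show 0.127, 0.120 or 0.107.

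**Without the constant rate.** Let u be the share of all controls first exposed after month 6. CACE recovers (1 − c − u) / (1 − c). For c = 10% and u = 5%, 10% or 20%, that is 94%, 89% or 78%. Over c and u each from 5% to 20%, it is 75% to 95%.

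**The case against.** Several stronger readings are tempting, and the documents do not support them.

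- **That the tests of all three hypotheses misclassify controls.** A reader might infer this because each hypothesis names 12 months. The tests in Section 13.1 rest on randomised condition, which classes nobody by exposure. Late contamination dilutes that comparison but does not misclassify anyone in it. For Aim 3, the lagged model does use the later outcome ("we can examine the effect of baseline randomization to treatment status on 12-month counts of injection initiation as the outcome"), but no contamination adjustment is stated for it, so late exposure there is simply unadjusted.
- **That nearly half of exposed controls are missed.** Under a constant rate, the missed share of ever-exposed controls is (1 − c) / (2 − c), or 49%, 47% and 44% for the three scenarios. It is close to one half for any small c, because it follows from assuming equal rates in two equal windows. It does not measure the harm; the attenuation in the table does.
- **That the gap could produce a false claim of efficacy.** If exposure is protective, missing some of it leaves the estimate between the unadjusted comparison and full correction.
- **That the items are certainly absent at 12 months.** Appendix I, which holds the follow-up domains, is listed but its content is not available. That is a reason to check it, but it does not override the wording of 3.19.

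Two objections to a simple repeat of the items stand. The 6-month interview puts the intervention's phrases to controls, so recognising one at 12 months may reflect the interview rather than spillover. And exposure reported for months 6 to 12 is concurrent with the 12-month outcome: people who are being asked to initiate others may also talk more about initiation. A month-6 measure precedes that outcome. Both objections shape the fix.

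**Conclusion.** The gap is real but limited. As written, the CACE analyses of the 12-month counts for Aims 1 and 2 under-correct for contamination that begins after month 6. Controls already recorded as exposed at month 6 remain correctly identified as exposed, and the 6-month outcomes are untouched. In the constant-rate scenarios the loss is about 5%, 10% or 20% of the true 12-month difference. For those exposure shares this is an upper bound, because it gives second-hand conversation the full effect of a one-hour session across the whole outcome window. The contamination shares, their timing and the independence of exposure from baseline risk are assumptions. Sample size, alpha and stated power are not affected. This is a cheap improvement to an additional analysis, not a flaw in the main comparison.

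**What to change.** 1. Add contamination items to the 12-month interview, after the outcome items, with recall limited to the past six months. Base them on the masked conversation questions. Do not count 12-month recognition of an intervention phrase as exposure by itself.
2. In Section 13.1, define the exposure class for the 6-month outcome from the month-6 answers only, and for the 12-month outcome from a report at either visit.
3. Report the 12-month CACE with the month-6-only class as a sensitivity analysis, because exposure in months 6 to 12 is concurrent with the outcome.
4. Check Appendix I. If it already lists these items at 12 months, reconcile it with 3.19. Correct the reference to Section 3.5.17.3 in the same edit.

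The cost is a few minutes of an interview already planned, a small questionnaire change and one more sensitivity analysis. Some priming from the 6-month interview and some concurrent-reporting error may remain. No change to sample size is needed.
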